			-11:30	20:30	Snack (voluntary)								
		1	-0:30	07:30	High-fat, high caloric breakfast	A ^{2, 9,}	\mathbf{x}^2		\mathbf{x}^2	\mathbf{x}^2	\mathbf{x}^2		
			0:00	08:00	BI 1358894 administration								
			0:30	08:30			Х			X	х		
			1:00	09:00			Х		X	X	Х		
			1:30	09:30			Х			X	X		
7			2:00	10:00	240 mL fluid intake		X			X	X		
ne)			2:30	10:30			X						
alc			3:00	11:00			X			X	X		
Period 1: Treatment R (BI 1358894 alone) 7			4:00	12:00	240 mL fluid intake, thereafter lunch ³		X		X	X	X		
135			6:00	14:00			X			X	X		
BI			7:00	15:00			X			X	X		
R (8:00	16:00	Snack (voluntary) ³		X			X	X		
sut			10:00	18:00	Dinner		X						
tme			12:00	20:00			X		X	X	X		
rea		2	16:00	24:00		B ⁹	X			X			
: T		2	24:00 34:00	08:00 18:00		B	X		X	X	X		
l bo		3	48:00	08:00			X X		v	X X	X X		
eric		4	72:00	08:00	Breakfast (voluntary),	B^9	X		X X	X	X	X	X
P		'	72.00	00.00	discharge from trial site ⁸		A		A	A	A	Α .	A
		5	96:00	08:00	Ambulatory visit		х		X	X	х		
		6	120:00	08:00	Ambulatory visit		X			X	X		
		7	144:00	08:00	Ambulatory visit		X			X	X		
		8	168:00	08:00	Ambulatory visit		X			X	X		
		9	192:00	08:00	Ambulatory visit	B^9	X			X	X		
		11	240:00	08:00	Ambulatory visit	_ 0	X			X	X		
		14	312:00	08:00	Ambulatory visit	B^9	X			X	X		

c25796375-03 Trial Protocol

Page 5 of 91

Proprietary confidential information © 2019 Boehringer Ingelheim International GmbH or one or more of its affiliated companies

FLOW CHART (continued)

Period	Visit	Day	Planned time (relative to first BI 1358894 administration) [h:min]	Approximate clock time of actual day [h:min]	Event and comment	Safety laboratory ⁹	PK blood BI 1358894 and metabolite	PK blood itraconazole	12-lead ECG	Vital signs (BP, PR)	Questioning for AEs and concomitant therapy ⁶	Physical and neurological examination	C-SSRS
	3	-3	-72:00	08:00	Ambulatory visit,								
		-2	-48:00	08:00	itraconazole administration Ambulatory visit, itraconazole administration								
		-1	24:00	08:00	Ambulatory visit, itraconazole administration								
			-12:00	20:00	Admission to trial site	x ⁵					X		
			-11:30	20:30	Snack (voluntary)								
		1	-2:30	05:30		B ^{2, 9}	x^2	x^2	x ²	\mathbf{x}^2	x ²		
			-1:30	06:30	Itraconazole administration								
			-0:30	07:30	High-fat, high-caloric breakfast								
7			0:00	08:00	BI 1358894 administration	-							
le)			0:30	08:30			X			X	X		
azo			1:00	09:00 09:30		+	X		X	X	X		
cons			2:00	10:00	240 mL fluid intake		X			X	X		
trac			2:30	10:00	240 IIIL Huid Illiake		X			X	X		
+ 1.			3:00	11:00			X			X	X		

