- 2. The time is approximate; the procedure is to be performed and completed within the 2 h prior to drug administration (Period 1) / within 2.5 h prior to BI 1358894 administration (Period 2).
- 3. If several actions are indicated at the same time, the intake of meals will be the last action.
- 4. End of trial examination (performed 11 to 17 days after last itraconazole and 21 to 27 days after last BI 1358894 administration) includes: physical examination, neurological examination, body weight, vital signs, ECG, safety laboratory, recording of AEs and concomitant therapies, and suicidality assessment (C-SSRS).
- 5. Only urine drug screening and alcohol breath test will be done at this time.
- 6. AEs and concomitant therapies will be recorded throughout the trial, but will be specifically asked for at the times indicated in the Flow Chart above. Headaches will be recorded with the data given in Section 6.2.2.
- 7. Treatments R and T are to be separated by a wash-out interval of at least 17 days between administrations of BI 1358894.
- 8. Discharge from trial site fitness assessment includes: physical examination, neurological examination, ECG, vital signs, recording of AEs, suicidality assessment (C-SSRS), and concomitant therapies.
- 9. Letters A, B, and C define different sets of safety laboratory examinations (see Section 5.2.3). Safety laboratory examination A to be taken and medically evaluated within 3 days before first administration of BI 1358894. This can be omitted if screening examination is performed on Days -3, -2 or -1 of treatment period 1.
- 10. Blood sample for pharmacogenetic assessment.

c25796375-03 Trial Protocol

Page 7 of 91

Proprietary confidential information © 2019 Boehringer Ingelheim International GmbH or one or more of its affiliated companies

TABLE OF CONTENTS

TI	TLE I	PAGE.	•••••		1
CL	INIC	AL TR	IAL PR	OTOCOL SYNOPSIS	2
				ΓS	
AB	BRE	VIATIO	ONS		12
1.	INT	RODU	CTION	[16
	1.2	DRUG		LE	
		1.2.1		894	
			1.2.1.1	Nonclinical pharmacology	
			1.2.1.2	J 1 8J	
			1.2.1.3	63	

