	Free T4 – Thyroxine	X		X
Substrates	Glucose (Plasma)	X	X	X
	Creatinine	X	X	X
	Bilirubin, Total	X	X	X
	Bilirubin, Direct	X	X	X
	Protein, Total	X	X	X
	Albumin	X	X	X
	Albumin (Protein Electrophoresis)	X		
	Alpha-1-Globulin (Protein Electrophoresis)	X		
	Alpha-2-Globulin (Protein Electrophoresis)	X		
	Beta-Globulin (Protein Electrophoresis)	X		
	Gamma-Globulin (Protein Electrophoresis)	X		
	C-Reactive Protein (CRP) (Quant)	X	X	X
	Uric Acid	X	X	X
	Cholesterol, total	X	X	X
	Triglyceride	X	X	X

Proprietary confidential information © 2019 Boehringer Ingelheim International GmbH or one or more of its affiliated companies

Table 5.2.3: 1 Routine laboratory tests (cont.)

Functional lab group	Test name [comment/abbreviation]	A	В	С
Electrolytes	Sodium	X	X	X
-	Potassium	X	X	X
	Chloride	X	X	X
	Calcium	X	X	X
	Phosphate (as Phosphorus, Inorganic)	X	X	X
Urinalysis (Stix)	Urine Nitrite (qual)	X	X	X
	Urine Protein (qual)	X	X	X
	Urine Glucose (qual)	X	X	X
	Urine Ketone (qual)	X	X	X
	Urobilinogen (qual)	X	X	X
	Urine Bilirubin (qual)	X	X	X
	Urine Erythrocytes/hemoglobin	X	X	X
	Urine WBC/Leucocytes (qual)	X	X	X
	Urine pH	X	X	X
Urine sediment	Only positive findings will be reported (for instance, the			
(microscopic	presence of sediment bacteria, casts in sediment, squamous			
examination if	epithelial cells, erythrocytes, leukocytes)			
erythrocytes,				
leukocytes nitrite or				
protein are abnormal				
in urine)				

A: parameters to be determined at Visit 1 (screening examination) and at Visit 2 Day 1 (if screening had been earlier than 3 days prior)

B: parameters to be determined at Visit 2 on Days 2, 4, 9, 14 and at Visit 3 on Days 1, 2, 4, 9, 14 (for time points refer to Flow-Chart)

C: parameters to be determined at Visit 4 (end of trial examination).

The tests listed in Table 5.2.3: 2 are exclusionary laboratory tests that may be repeated as required. The results will not be entered in the CRF/database and will not be reported in the CTR. Except for drug screening, it is planned to perform these tests during screening only. Drug screening will be performed at screening and prior to each treatment period.

Trial Protocol

Page 53 of 91

Proprietary confidential information © 2019 Boehringer Ingelheim International GmbH or one or more of its affiliated companies

Table 5.2.3: 2 Exclusionary laboratory tests

Functional lab group	Test name
Drug screening (urine)	Amphetamine/MDA Barbiturates
	Benzodiazepine Cannabis Cocaine

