7.3.4 Safety analyses

Safety will be analysed based on the assessments described in Section 2.2.2.2. All treated subjects (TS, refer to Section 7.2) will be included in the safety analysis. Safety analyses will be descriptive in nature and based on BI standards. No hypothesis testing is planned.

For all analyses, the treatment actually administered (= treatment at onset) to the subject will be used (any deviations from the randomised treatment will be discussed in the minutes of the Report Planning Meeting).

Treatments will be compared in a descriptive way. Tabulations of frequencies/proportions will be used to evaluate categorical (qualitative) data, and tabulations of descriptive statistics will be used to analyse continuous (quantitative) data.

Measurements (such as ECG, vital signs, or laboratory parameters) or AEs will be assigned to treatments (see Section 4.1) based on the actual treatment at the planned time of the measurement or on the recorded time of AE onset (concept of treatment emergent AEs). Therefore, measurements planned or AEs recorded prior to first intake of trial medication will be assigned to the screening period, those between first intake of BI 1358894 until end of residual effect period (14 days) in period 1 are attributed to the treatment interval "BI 1358894 alone". Events after the residual effect period of BI 1358894 but prior to first intake of itraconazole will be assigned to "BI 1358894 follow-up". Events between first intake of itraconazole in period 2 and administration of BI 1358894 in period 2 are attributed to the treatment interval "itraconazole alone" and those occurring between treatment with BI 1358894 and itraconazole in period 2 and end of residual effect period of itraconazole (6 days) after last intake of itraconazole or end of residual effect period of BI 1358894 (14 days) after BI 1358894 intake, whatever occurs first, are attributed to the treatment interval "BI 1358894 + itraconazole". Events after the treatment interval "BI 1358894 + itraconazole" but before trial termination date are assigned to "BI 1358894 + itraconazole follow-up". These assignments including the corresponding time intervals will be defined in detail in the TSAP. Note that AEs occurring after the individual subject's end of trial but entered before final database lock will be reported to Pharmacovigilance only and will not be captured in the trial database.

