6.7 BASELINE, TIME WINDOWS AND CALCULATED VISITS

The baseline value is defined as the last measurement before administration of BI 1358894 in each period.

Section 6.1 of the CTP: Exact times of measurements outside the permitted time windows will be documented. The acceptable time windows for screening and the end of trial examination are provided in the CTP Flow Chart.

Study measurements and assessments scheduled to occur 'before' BI 1358894 administration on Day 1 of Period 1 are to be performed and completed within a 2 h-period prior to BI 1358894 administration. Study measurements and assessments scheduled to occur 'before' itraconazole administration on Days -3 to -1 and 2 to 11 of Period 2 are to be performed and completed within a 2 h-period prior to itraconazole administration. Study measurements and assessments scheduled to occur 'before' BI 1358894 administration on Day 1 of Period 2 are to be performed and completed within a 1.0 h-period prior to itraconazole administration.

In visits 2 and 3, the acceptable deviation from the scheduled time for vital signs, ECG, and laboratory tests will be \pm 45 min on Day 1, \pm 60 min on Day 2, and \pm 120 min from Day 3 onwards.

[...]

Starting from 48 hours after BI 1358894 administration (and beyond) a time window of \pm 120 min will be allowed for pharmacokinetic blood sampling times.

Adherence to time windows will be checked via the consistency check listings at the RPM.

Unscheduled measurements of laboratory data and vital signs data will be assumed to be repeat measurements of the most recent scheduled measurement (e.g. for follow-up or confirmation of a particular value). Therefore, unscheduled measurements will be assigned to the planned time point of the previous scheduled measurement.

Proprietary confidential information © 2019 Boehringer Ingelheim International GmbH or one or more of its affiliated companies

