7.8.2 Laboratory data

The analyses of laboratory data will be descriptive in nature and will be based on BI standards [001-MCG-157] (10).

Laboratory data will be analysed qualitatively via comparison of laboratory data to their reference ranges. Values outside the reference range as well as values defined as possibly clinically significant will be flagged in the data listings.

Clinically relevant findings in laboratory data will be reported as baseline conditions (at screening) or as AEs (during the trial) if judged clinically relevant by the investigator, and will be analysed as such.

It is the investigator's responsibility to decide whether a lab value is clinically significantly abnormal or not (at the RPM/DBLM at the latest).

Descriptive statistics of laboratory data will be calculated by planned time point based on the worst value of the subject at that planned time point (or assigned to that planned time point).

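### Under SAP 6.7, an unscheduled lab or vital-sign reading taken on itraconazole alone would be booked to the Period 1 312 h time point of BI 1358894 alone

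*SAP*

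**What the plan says.** SAP 6.7 (Baseline, time windows and calculated visits) treats all unscheduled laboratory and vital-sign readings alike. They "will be assumed to be repeat measurements of the most recent scheduled measurement", and on that assumption "unscheduled measurements will be assigned to the planned time point of the previous scheduled measurement". Nothing restricts the rule to the same period, to a maximum delay, or to readings taken before another drug is started.

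Four other places determine what the rule does:

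- **Schedule.** The last Period 1 row of the Flow Chart is Day 14, "312:00 08:00 Ambulatory visit", with safety laboratory panel B and vital signs. Table 5.2.3: 1 of the protocol sets panel B "at Visit 2 on Days 2, 4, 9, 14 and at Visit 3 on Days 1, 2, 4, 9, 14". On Days -3 to -1 of Period 2 the Flow Chart shows "Ambulatory visit, itraconazole administration" but no safety laboratory test and no vital signs. The Day -1 evening mark in the laboratory column carries a footnote: "Only urine drug screening and alcohol breath test will be done at this time".
- **Treatment label.** Protocol 7.3.4 assigns measurements to treatments "based on the actual treatment at the planned time of the measurement". It counts the 14 days after the Period 1 dose as 'BI 1358894 alone' and defines a separate itraconazole-alone interval.
- **Value summarised.** SAP 7.8.2 summarises laboratory data "by planned time point based on the worst value of the subject at that planned time point", and SAP 7.8.3 uses the last vital-sign value. Both expressly include values assigned to the time point.
- **Phases.** SAP Table 6.1: 2 has an 'ITZ' phase, but it is defined for adverse events only.

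**The concern.** Treating an unscheduled reading as a repeat of the last scheduled one is reasonable while the subject's treatment has not changed. It stops being reasonable once a new drug has been given. Here the scheduled measurements have a gap, and the whole run-in on itraconazole lies inside it apart from its last 2.5 h. A laboratory or vital-sign reading prompted by something seen on itraconazole would be carried back into the other period and appear as a late value of the reference treatment.

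Such readings are foreseeable. Subjects attend the site on Days -3, -2 and -1. The protocol allows retests (5.2.3), asks for clinically relevant abnormal values to be monitored until acceptable (6.2.3), and provides for unscheduled liver tests when symptoms suggest hepatic injury (5.2.6.1.4).

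At stake is the attribution of individual safety values. Protocol 7.3.4 separates itraconazole alone from BI 1358894 alone, and the rule in SAP 6.7 can undo that separation for laboratory and vital-sign summaries.

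**Working it through.** The check is a timeline, with the Period 1 dose of BI 1358894 at 0 h.

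**1. The plan's own figures.** Day 14 is (14 - 1) x 24 = 312 h. The 14-day residual effect period is 14 x 24 = 336 h, as SAP Table 6.1: 2 states. Since 312 < 336, the 312 h time point lies inside 'BI 1358894 alone'.

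**2. Period 2 on the same clock, at the minimum 17-day wash-out** (Protocol 3.1):

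- Period 2 dose of BI 1358894: 17 x 24 = 408 h
- first itraconazole dose (-72:00): 408 - 72 = 336 h
- scheduled pre-dose laboratory test and vital signs (-2:30): 408 - 2.5 = 405.5 h

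**3. Applying SAP 6.7.** Each test reading takes the latest scheduled time at or before it. The result is the same for laboratory tests and vital signs.

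| Unscheduled reading (h) | Relative to Period 2 dose (h) | Assigned to (h) |
|---|---|---|
| 337 | -71 | 312 (Period 1) |
| 360 | -48 | 312 (Period 1) |
| 384 | -24 | 312 (Period 1) |
| 396 | -12 | 312 (Period 1) |
| 405 | -3 | 312 (Period 1) |
| 407 | -1 | 405.5 (Period 2 pre-dose) |

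**4. How much of the itraconazole-alone interval is affected.** The interval lasts 408 - 336 = 72 h. The affected part is 405.5 - 336 = 69.5 h, and 69.5/72 = 96.5%. This does not depend on the length of the wash-out, because both limits are fixed relative to the Period 2 dose.

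**5. How far back a reading is carried, and how much of the unscheduled gap is on itraconazole.** Both depend on the wash-out, for which the protocol gives only a minimum. The 21- and 28-day rows are assumptions.

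| Wash-out (days) | Delay after 312 h for readings on itraconazole (h) | Itraconazole share of the gap |
|---|---|---|
| 17 | 24 to 93.5 | 69.5/93.5 = 74% |
| 21 | 120 to 189.5 | 69.5/189.5 = 37% |
| 28 | 288 to 357.5 | 69.5/357.5 = 19% |

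**6. When a reading changes a summary.** A laboratory value replaces the scheduled 312 h value only if it is worse (SAP 7.8.2). A vital-sign value replaces it whenever it is the last one assigned there, normal or not (SAP 7.8.3).

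**7. Size for one value.** If one subject's summarised value rises by d, the mean of 16 subjects rises by d/16. For assumed d of 30 and 60 units this is 30/16 = 1.9 and 60/16 = 3.75 units. The documents give no figure for d or for how often such readings occur.

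**The case against.** The strongest reply is that the rule is doing its job. SAP 6.7 has follow-up or confirmation of a value in mind. A recheck of an abnormal Day 14 sample concerns a finding that arose after BI 1358894 alone, and under the worst-value rule it leaves the 312 h summary unchanged unless it is worse. That is fair for many rechecks taken before itraconazole starts. It does not cover a reading prompted by something new on itraconazole, or a recheck that has worsened after itraconazole was started.

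Second, the safety signal is not lost. Clinically relevant findings are reported as adverse events and placed by actual onset. Out-of-range laboratory values are flagged in the listings, and SAP 7 sorts individual values by actual treatment where appropriate. This stands, and it limits the consequence to the summaries.

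Third, SAP 7.8.2 and 7.8.3 specify summaries by planned time point and describe no treatment column. The SAP refers treatment handling to an analysis dataset plan that was not available for this check. How the final tables would label such a reading is therefore not fully established. What is established is the assignment to Period 1, 312 h, and the statement in Protocol 7.3.4 that the label follows the planned time. The list of changes in SAP 4 leaves that statement alone.

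A reader might go further and infer that the reference column will be inflated and the contrast between test and reference reduced. The documents do not support that. They give no rate of unscheduled readings, a laboratory value counts only if it is worse, and under the last-value rule a vital-sign summary can move either way. Nor is 74% a probability: it is a share of clock hours at the shortest wash-out allowed.

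**Conclusion.** The gap in the rule is real, and its effect is conditional. As written, any unscheduled laboratory or vital-sign reading in the first 69.5 h of the 72 h itraconazole-alone interval is assigned to Period 1, 312 h, a time point that the protocol attributes to BI 1358894 alone. An adverse event with the same onset would go to 'ITZ'. The two displays could then attribute the same episode to different treatments. That would follow from their different bases, and it is a possibility rather than a certain contradiction.

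The conclusion assumes that the Flow Chart and Table 5.2.3: 1 are the full schedule. Protocol 6.1 gives a window for assessments before itraconazole on Days -3 to -1, but neither source schedules a safety laboratory test or vital signs on those days. It also assumes that the 312 h visit took place; if it was missed, the reading might be assigned to an earlier Period 1 time point.

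The reach is limited to descriptive safety summaries. The PK endpoints and their confidence intervals are unaffected, ECGs are outside the rule, and adverse events follow actual onset. The point deserves correction because a stated rule gives the wrong attribution and the remedy costs almost nothing. The main result of the trial is not at risk.

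**What to change.** Add to SAP 6.7: an unscheduled laboratory or vital-sign reading is assigned to the previous planned time point only if no new study drug (the first itraconazole dose or a dose of BI 1358894) was given between that time point and the reading. Otherwise it is labelled by the actual treatment at its date and time, for example in an 'ITZ, unscheduled' row, or listed only. In either case it stays out of the time-point summary of another treatment.

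The condition should be the next new drug, not the adverse event phase of Table 6.1: 2. With a wash-out longer than 17 days, a genuine repeat of the 312 h sample taken after 336 h but before itraconazole falls in the 'F/U BI' phase. A phase-based condition would remove it from 312 h although no new drug had been given.

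The cost is one sentence in the SAP and one condition in the analysis dataset, using dosing and measurement times. No new data are needed.

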7. PLANNED ANALYSIS

Safety analysis (refer to Section 7.8) will be performed by and will be presented in Sections 15.1 to 15.4 of the CTR and in Appendix 16.2 and 16.1.13.1.

Inferential statistical analyses of PK endpoints (refer to Section 7.4, Section 7.5.2 and Section 7.6) will also be performed by and will be presented in Section 15.5 of the CTR and in Appendix 16.1.13.3.

Descriptive data analysis of PK endpoints and concentrations will be performed by the department Translational Medicine and Clinical Pharmacology (TMCP) at BI and will be presented in Section 15.6 of the CTR.

The format of the listings and tables will follow the standards defined in the BI corporate guideline "Reporting of Clinical Trials and Project Summaries" [001-MCG-159] (6) with the exception of those generated for PK-calculations (7).

The individual values of all subjects will be listed, sorted by treatment sequence, subject number, visit and actual treatment (if appropriate).

The listings will be included in Appendix 16.2 of the CTR.

For end-of-text tables, the set of summary statistics for non-PK parameters is:

N number non-missing observations

Mean arithmetic mean SD standard deviation

Min minimum Median median Max maximum

For analyte concentrations, the following descriptive statistics will additionally be calculated:

CV arithmetic coefficient of variation

gMean geometric mean

gCV geometric coefficient of variation

For PK parameters, the following descriptive statistics will additionally be calculated:

CV arithmetic coefficient of variation

gMean geometric mean

gCV geometric coefficient of variation

P10 10th percentile Q1 1st quartile Q3 3rd quartile P90 90th percentile

Proprietary confidential information © 2019 Boehringer Ingelheim International GmbH or one or more of its affiliated companies

The data format for descriptive statistics of concentrations will be identical to the data format of the respective concentrations. The descriptive statistics of PK parameters will be calculated using the individual values with the number of decimal places as provided by the evaluation program. Then the individual values as well as the descriptive statistics will be reported with three significant digits in the CTR.

Tabulations of frequencies for categorical data will include all possible categories and will display the number of observations in a category, as well as the percentage (%) for each treatment sequence/group. Percentages will be rounded to one decimal place and will be based on all subjects in the respective subject set whether they have non-missing values or not. The category 'missing' will be displayed only if there are actually missing values.

Units of variables should be given in the titles or column/row descriptors in square brackets (e.g. [mg]).

Exclusion of PK parameters

The ADS ADPP (PK parameters) contains column variables indicating inclusion/exclusion (APEXC) of a PK parameter and an analysis flag comment (APEXCO). All analyses based on the PKS will include parameters if they are not flagged for exclusion, that is APEXCO is equal to "Included".

Exclusion of PK concentrations

The ADS ADPC (PK concentrations per time-point or per time-interval) contains column variables ACEXC and ACEXCO indicating inclusion/exclusion (ACEXC) of a concentration and an analysis flag comment (ACEXCO). Exclusion of a concentration depends on the analysis flag comment ACEXCO. For example, if ACEXCO is set to 'ALL CALC', the value will be excluded for all types of analyses based on concentrations. If ACEXCO is set to 'DESC STATS' the value will be excluded from descriptive evaluations per planned time point/time interval. If ACEXCO contains the addition 'TIME VIOLATION' or 'TIME DEVIATION' the value can be used for further analyses based on actual times. If ACEXCO is set to 'HALF LIFE', the value will be excluded from half-life calculation (and, as a consequence, any calculation that relies on λ_z) only; the value is included for all other analyses.

Further details are given in 001-MCS-36-472_RD-01 "Noncompartmental Pharmacokinetic / Pharmacodynamic Analyses of Clinical Studies" (5) and 001-MCS-36-472_RD-03 "Description of Analytical Transfer Files and PK/PD Data Files" (11).

